#### 5.0 Measures

#### **5.1 Outcome Measures**

Clinician-Administered PTSD Scale for DSM-5 (CAPS-5)

PTSD Checklist for DSM-5 (PCL): last month, since last visit, since last week

Beck Depression Inventory-II (BDI-II)

Emotional Regulations Questionnaire (ERQ)

Interpersonal Reactivity Index (IRI)

Pittsburgh Sleep Quality Index (PSQI)

Post Traumatic Growth Inventory (PTGI)

Toronto Alexithymia Scale (TAS-20),

Quality of Relationships Inventory (QRI)

Significant Others' Responses to Trauma Scale (SORTS)

Revised Conflicts Tactics Scale (CTS2)

Inventory of Psychosocial Functioning (IPF)

Miller Social Intimacy Scale (MSIS)

The Trauma and Attachment Beliefs Scale (TABS)

Multiscale Dissociation Inventory (MDI)

Interpersonal Closeness Measure (IPC)

Couples Satisfaction Index (Romantic couples only) (CSI)

#### **5.2 Process Measures**

Reactions to Research Participation Questionnaire (RRPQ)

MP-12 Statistical Analysis Plan Version 1: 26 February 2016

Long-term Follow-up Questionnaire (LTFUQ)

## **5.3 Safety Measures**

Vitals (blood pressure, pulse, body temperature)

Somatic Symptoms

Subjective Units of Distress (SUD)

Columbia Suicide Severity Rating Scale (C-SSRS)

General Well-being (GWB)

Spontaneously Reported Reactions (SRR)

Adverse Events (AEs)

## 6.0 Analyses

In general, nominal variables will be described in terms of frequencies and percentages and analyzed using chi square analysis. Ordinal and non-normal continuous variables will be described using sample median and range, and analyzed by non-parametric statistical tests, and approximately normal variables will be described using sample mean and standard deviations and analyzed by parametric statistical tests. All statistical tests will be two-sided and a difference resulting in a p-value of less than or equal to 0.05 will be considered statistically significant. All p-values will be rounded to and displayed in four decimals. P-value less than 0.0001 will be shown in tables as <0.0001. For any analysis that is called out as parametric, e.g. t-test, the parametric assumptions will be examined. If necessary, nonparametric analyses will be utilized, e.g. Wilcoxon rank-sum test.

Clinical data will be presented in tabular format. Data not subject to analysis according to this plan will not appear in any tables or graphs but will be included in the data listings. Analyses will be carried out with SAS Version 9.4 (or higher). Selected results may be presented graphically using standard graphical software.

Post-hoc exploratory analyses not identified in this SAP may be performed to further examine the study data. These analyses will be clearly identified as such in the final clinical study report.

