6.2 Preparation and Administration

In this study, 10 dyads will receive MDMA in an open-label fashion.

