Qualitative safety analyses will examine adverse events, concomitant medications, and spontaneously reported reactions by summary tables listing maximum severity and

duration, as well as frequencies and percentages, tabulated overall and by PTSD+ participants and CSO participants. Quantitative safety analyses will examine vital signs, changes in Tinnitus and/or Pain, SUD, and C-SSRS, with comparisons made between by PTSD+ participants and CSO participants for effect of PTSD on safety measures.

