12.1 Statistical Power

This pilot RCT is the first study of its kind intended to establish preliminary effect size estimates of CBCT combined with MDMA-assisted psychotherapy for PTSD. In the absence of published effect sizes for this new treatment modality, effect sizes were estimated based on prior trials of these individual treatments. In a limited number of small pilot studies, CBCT for PTSD yielded paired-treatment effect sizes of g > 1.0 for improvements in PTSD on the primary outcome measure and co-morbid symptoms. The two completed controlled RCTs of MDMA-assisted psychotherapy for PTSD have yielded effect sizes of g > 1.0 for improvements in PTSD symptoms as well. Assuming that effect size of the combined treatment may be approximately 0.8, estimated power for a within-subject analysis with a significance level of .05 based on a 2-tailed test, is 62% for a sample size of 10 participants for the primary measure, suggesting the potential for an underpowered design, but with some possibility of detecting a within-subject effect due to treatment. Statistical power estimates were not available for secondary and exploratory measures, as they were previously not used in sponsor-supported studies.

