## Columbia Suicide Severity Rating Scale (C-SSRS)

Suicidal ideation and behavior will be summarized according to suggestions made in the Columbia-Suicide Severity Rating Scale Scoring and Data Analysis Guide [5][5]. A positive response for suicidal ideation is counted when subjects respond "yes" to any one of the five suicidal ideation questions (Categories 1-5) on the C-SSRS (i.e. a score > 0 for suicidal ideation score). Serious suicidal ideation is a suicidal ideation score of 4 or 5. A positive response for suicidal behavior occurs when subjects answer "yes" to any one of the five suicidal behavior questions (Categories 6-10) on the C-SSRS (i.e. a score > 0 for suicidal behavior score). The number and percent of positive responses of Positive Ideation, Serious Ideation, and Positive Behavior will be tabulated overall and by PTSD+ participants and CSO participants for each time period. Lifetime serious suicidal ideation and positive behavior frequencies will be compared to cumulative frequencies at all timepoints throughout the study.

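### The SAP's default chi-square test does not fit the nominal comparisons the documents call for, which are paired, with 10 pairs and mostly sparse cells

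*SAP*

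**What the plan says.** SAP 6.0 sets a general rule: "nominal variables will be described in terms of frequencies and percentages and analyzed using chi square analysis". The same paragraph adds "All statistical tests will be two-sided and a difference resulting in a p-value of less than or equal to 0.05" as the criterion for statistical significance. No later SAP section replaces chi-square with another test for categorical data.

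The trial has one arm: "In this study, 10 dyads will receive MDMA in an open-label fashion" (Protocol 6.2). Two places call for a comparison to which the nominal rule would apply:

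- The SAP section on the C-SSRS reduces the scale to positive or negative ideation, serious ideation and behaviour, and then states: "Lifetime serious suicidal ideation and positive behavior frequencies will be compared to cumulative frequencies at all timepoints throughout the study". Both sets of frequencies come from the same people.
- Protocol 12.0 lists vital signs, tinnitus or pain, SUD and C-SSRS for quantitative safety analysis, "with comparisons made between by PTSD+ participants and CSO participants for effect of PTSD on safety measures". The two roles are the two members of each dyad.

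**The concern.** Read in the ordinary way, chi-square analysis means the Pearson test. It treats the two sets of yes/no answers as coming from unrelated people, and it relies on a large-sample approximation. Neither condition is met for a comparison within a person or within a dyad with 10 pairs.

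At stake is a printed p-value on suicidality. The protocol invites reading the PTSD+ versus CSO contrast as an effect of PTSD, and a handful of events could carry a significance label that the data do not support. The stated 5% criterion would also not describe the test's actual error rate.

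**Working it through.** **The plan's own figure.** The only power figure concerns the continuous primary measure. Protocol 12.1 takes "Assuming that effect size of the combined treatment may be approximately 0.8", "with a significance level of .05 based on a 2-tailed test", and reports a power that "is 62% for a sample size of 10 participants for the primary measure". A paired t-test with 9 degrees of freedom and noncentrality 0.8 × √10 = 2.53 has power 61.6%, which reproduces it. The documents give no figure for any nominal test, so what follows does not touch this number.

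**Inputs.** From the documents: 10 dyads, two-sided 0.05, chi-square. Assumed, because the documents give neither: marginal rates of 0.2 to 0.5 and within-pair correlation (phi) of −0.2 to 0.5.

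**Expected counts.** With 10 per role and E events among 20 people, each 'yes' cell expects E/2 and each 'no' cell (20 − E)/2. All four reach 5 only when E is exactly 10. For uncommon events the 'yes' cells fall short.

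**Actual error rate.** All 286 possible paired 2×2 tables for 10 pairs were enumerated and weighted by their multinomial probabilities with equal marginal rates. Rejection rate at p ≤ 0.05, for rates 0.2 / 0.3 / 0.5:

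| phi | Pearson chi-square | Exact McNemar |
|---|---|---|
| −0.2 | 4.9% / 5.6% / 6.4% | 0.4% / 0.9% / 1.4% |
| 0 | 3.0% / 3.7% / 4.2% | 0.2% / 0.5% / 0.9% |
| 0.3 | 1.0% / 1.4% / 1.6% | 0.03% / 0.1% / 0.3% |
| 0.5 | 0.3% / 0.5% / 0.5% | 0.01% / 0.02% / 0.06% |

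The direction of the error follows the sign of the correlation. At phi = −0.4 and rate 0.5, Pearson reaches 8.7%.

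**A sparse table.** Suppose 4 of 10 PTSD+ and 0 of 10 CSO members are positive.

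- Pearson: 20 × (4×10 − 6×0)² / (10×10×4×16) = 5.0, p = 0.025.
- Fisher: 2 × C(10,4)/C(20,4) = 2 × 210/4845 = 0.087.
- Exact McNemar on 4 discordant pairs: 2 × 0.5⁴ = 0.125.
- Large-sample McNemar: (4 − 0)²/4 = 4, p = 0.046.

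The large-sample paired test is also below 0.05, and the exact unpaired test is already above it. Most of the gap is therefore due to small-sample approximation, not to ignoring the pairing.

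**Table layout.** The SAP does not say how paired answers would be tabulated. If they are cross-classified, chi-square tests association and not change. Five yes/yes and five no/no pairs (no change at all) give p = 0.0016. Six one-way changes with two yes/yes and two no/no give p = 0.43, where exact McNemar gives 2 × 0.5⁶ = 0.031.

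**The case against.** The strongest reply is that the rule is a general default tied to no named endpoint, and that the specific sections are mostly descriptive. Disposition has no inferential test. Demographics, medications and long-term follow-up items are summarised, and adverse events and vital signs above cutoff are tabulated. The C-SSRS sentence says frequencies will be compared but names no test or p-value. All of this stands, and it confines the point to the two comparisons quoted. It does not remove the point, because SAP 6.0 separates describing from analysing and supplies chi-square as the only method for the latter.

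A second reply is that chi-square analysis could include McNemar's version. The SAP does not say so, and elsewhere it names the Wilcoxon rank-sum test, an independent-samples method, as the fallback for its paired t-test.

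A third is that exact McNemar is far from 5% itself. That is correct: in the table above its size never exceeds 1.4%. It also needs at least 6 discordant pairs, since 5 give 2 × 0.5⁵ = 0.0625. It therefore cannot serve as a sensitive safety screen, and the remedy has to rest on the interval.

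A reader might infer that every nominal comparison in the trial is affected, or that chi-square is wrong in both directions in the tables the trial will produce. The first fails on the descriptive sections just listed. On the second, with 10 pairs Pearson is significant where exact McNemar is not in 36 of the 286 tables, and the reverse occurs in none. Missed differences against that comparator appear only if all 20 people are pooled (10 of 1,771 tables, against 152 of the other kind). One such table is 14 of 20 falling to 8 of 20 with 6 one-way changes: chi-square 0.057, exact McNemar 0.031. Pooling, however, ignores that the 20 people form 10 dyads. Counts of tables are also not probabilities.

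**Conclusion.** The default is wrong as written for the comparisons the documents call for, and it should be changed. The reason is textual and needs no assumed rate: the comparisons are within person or within dyad, cells will mostly be sparse, and neither document provides a test suited to either feature.

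The size does depend on assumptions. For 10 pairs and rates of 0.2 to 0.5, the nominal 5% test rejects in 0.3–1.6% of trials at correlation 0.3 to 0.5, 3.0–4.2% at 0, and 4.9–6.4% at −0.2. With zero or positive correlation it is conservative in the long run, so a general claim of inflated false positives is not supported. What can be said is that the stated 5% does not describe the test, and that individual sparse tables can be labelled significant when exact tests disagree.

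It might also seem that a better test would reveal a real shift between lifetime and on-study suicidality. The documents do not support that use: a lifetime history is set against participation of about 8 months (Protocol 4.1), so unequal observation windows alone would favour more lifetime positives.

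The consequence is limited to safety and exploratory results. The primary CAPS-5 paired t-test and its 62% power do not change.

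**What to change.** In SAP 6.0, replace chi-square for nominal variables with text such as:

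*Nominal safety data are summarised descriptively. Where a PTSD+ versus CSO or within-person comparison is made, it will use the paired difference in proportions with a 95% confidence interval and the exact McNemar test. PTSD+ versus CSO comparisons use the 10 dyads as pairs; within-person comparisons are made within role (10 pairs) and not pooled over the 20 participants. A non-significant result will not be read as absence of a safety difference.*

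In the C-SSRS section, state that lifetime versus on-study frequencies are descriptive only, because the observation windows differ.

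The cost is a few sentences in the SAP and a standard SAS option. The downside is that the exact test will rarely reach 0.05 with 10 pairs, so the report should lead with the paired difference and its interval.

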## 1. Primary Efficacy Analyses

The primary efficacy evaluation is a paired t-test of CAPS-5 Total Severity scores at baseline and the primary endpoint (visit 16) at an alpha level of 0.05. If the parametric assumptions for t-test analyses are not met, the analogous nonparametric methods will be used (Wilcoxon Rank-Sum).

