## 2. Secondary and Exploratory Efficacy Analyses

Efficacy of secondary and other exploratory outcome measures will be assessed at baseline, midpoint (visit 9), and primary endpoint (visit 16) to examine change in scores over time in the total sample, and separately, by PTSD+ participants and CSO participants.

For each model, a one-way repeated-measures ANOVA with post-hoc contrast comparisons will be conducted to test the effects of the treatment on: PTSD CAPS-5; Significant Others' Responses to Trauma Scale (SORTS); Posttraumatic Stress Disorder Checklist for the DSM-5 (PCL-5); Beck Depression Inventory-II (BDI-II); Emotion Regulation Questionnaire (ERQ); Pittsburgh Sleep Quality Index (PSQI); Posttraumatic Growth Inventory (PTGI); Toronto Alexithymia Scale-20 (TAS-20); Inventory of Psychosocial Functioning (IPF); Revised Conflict Tactics Scale (CTS-2); Trauma and Attachment Beliefs Scale (TABS); and Multiscale Dissociation Inventory (MDI). Relationship distress outcome measures include: Interpersonal Reactivity Index (IRI); Quality of Relationships Inventory (QRI); Miller Social Intimacy Scale (MSIS); Interpersonal Closeness Measure (IPC); and Couples Satisfaction Index (CSI).

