# 3. Secondary Efficacy Analyses at Secondary Endpoints (Long-Term Follow-up)

Efficacy of outcome measures for long-term follow-up will be assessed at baseline, midpoint (visit 9), primary endpoint (visit 16), 3-month follow-up (visit 17), and 6-month follow-up (Visit 18) to examine changes over time in the total sample, and separately, by PTSD+ participants and CSO participants.

For each model, a one-way repeated-measures ANCOVA with baseline scores as covariates and post-hoc contrast comparisons will be conducted to test the effects of the treatment on: PTSD CAPS-5; Significant Others' Responses to Trauma Scale (SORTS); Posttraumatic Stress Disorder Checklist for the DSM-5 (PCL-5); Beck Depression Inventory-II (BDI-II); Emotion Regulation Questionnaire (ERQ); Pittsburgh Sleep Quality Index (PSQI); Posttraumatic Growth Inventory (PTGI); Toronto Alexithymia Scale-20 (TAS-20); Inventory of Psychosocial Functioning (IPF); Revised Conflict Tactics Scale (CTS-2); Trauma and Attachment Beliefs Scale (TABS); and Multiscale Dissociation Inventory (MDI). Relationship distress outcome measures include: Interpersonal Reactivity Index (IRI); Quality of Relationships Inventory (QRI); Miller Social Intimacy Scale (MSIS); Interpersonal Closeness Measure (IPC); and Couples Satisfaction Index (CSI).

If data is missing from participant dropouts a mixed effect model repeat measures (MMRM) will be used instead of an ANCOVA.

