# 4. Additional Exploratory Analysis

Pearson Correlations will be computed between PTSD+ participants' CAPS-5 scores and CSO participants' outcomes (all) [4]. This analysis will be conducted for baseline, midpoint (visit 9), primary endpoint (visit 16), 3-month follow-up (visit 17), and primary endpoint (visit 18). Correlations (*r*) and *p* values will be reported to assess the direction and magnitude of these relationships. This analysis is intended to explore the potential impact of CSO participants' responses to the given treatment on PTSD+ participants' CAPS-5 scores over time.

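### The SAP gives every test the same 0.05 significance verdict and nowhere says that non-primary p-values are nominal, so chance findings among 16 secondary measures would be reported as statistically significant

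*SAP*

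**What the plan says.** SAP 6.0 opens with a rule of general scope. "All statistical tests will be two-sided", it says, and in the same sentence "a difference resulting in a p-value of less than or equal to 0.05 will be considered statistically significant".

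One primary test is named in efficacy section 1: "The primary efficacy evaluation is a paired t-test of CAPS-5 Total Severity scores at baseline and the primary endpoint (visit 16) at an alpha level". The level named there is 0.05.

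The other tests follow in three blocks:

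- **Section 2.** For each measure, "a one-way repeated-measures ANOVA with post-hoc contrast comparisons will be conducted to test the effects of the treatment on" a list made up of CAPS-5 and 16 questionnaires, over baseline, Visit 9 and Visit 16, in the total sample and in each role. The contrasts are not named, and nothing says whether they depend on the ANOVA or are adjusted.
- **Section 3.** The same list over five visits, by ANCOVA or MMRM, again "to examine changes over time in the total sample, and separately, by PTSD+ participants and CSO participants".
- **Section 4.** Pearson correlations, with p-values, of CAPS-5 in the PTSD+ participant against all CSO outcomes at five named visits.

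Protocol 12.0 applies .05 to all tests other than the PCL-5 and gives no other threshold for that scale. The SAP does not carry the exemption over. Neither document contains a testing order, gatekeeping, an alpha split, a correction, or a statement that non-primary p-values are descriptive. SAP 6.0 promises to flag only those exploratory analyses that the SAP does not itself list.

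**The concern.** A p-value of 0.04 on any questionnaire, in any of three samples, must be reported as statistically significant under the rule as written. With 16 measures and several overlapping analyses of each, some such results are to be expected when nothing has changed.

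This matters because Protocol 3.0 makes relationship functioning in both participants part of the overall objective, and only these secondary measures address it. SAP 2.0 says that the study's results will be preliminary data for designing a larger study. A reader who takes the list of significant measures at face value would be partly reading noise. The declared aim is estimation of effect sizes, yet the descriptive statistics listed under Efficacy Analyses include effect sizes and no confidence intervals.

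**Working it through.** **The plan's own figure.** Protocol 12.1 gives 62% power for the primary test with 10 participants: "Assuming that effect size of the combined treatment may be approximately 0.8", at "a significance level of .05 based on a 2-tailed test". Read as a standardised paired difference, the noncentrality is 0.8 × √10 = 2.53 on 9 degrees of freedom, and the exact noncentral t gives 61.6%. The stated figure reproduces. It covers the primary measure only; neither document states a family-wise error rate.

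**Counting tests.** Sixteen questionnaires are listed besides CAPS-5. Under the SAP, SORTS is a CSO measure and the other 15 are completed in both roles.

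- PTSD+ alone, baseline to Visit 16: 15.
- Both roles, baseline to Visit 16: 15 + 16 = 31.
- Omnibus ANOVAs of section 2 in three samples: 15 × 3 + 1 = 46.
- Adding the section 3 models: 46 + 46 = 92.
- Section 4: 16 CSO outcomes × 4 visits = 64, since Table 3 schedules no CAPS at Visit 9. Total 92 + 64 = 158.

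Subscales and post-hoc contrasts are not counted.

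**Independent tests.** The chance of at least one p ≤ 0.05 among m tests is 1 − 0.95^m: 53.7% for m = 15, 79.6% for m = 31, 90.6% for m = 46.

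**Correlated tests.** Questionnaires in the same people are correlated, which lowers these figures. The documents give no correlations, so they are assumed: between measures 0.5 (range 0 to 0.9), within dyad 0.3, between visits 0.5. Null trials of 10 dyads, in which no measure changes, were simulated.

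| Family | Tests | Independent formula | Correlation 0.5 | Correlation 0 to 0.9 |
|---|---|---|---|---|
| PTSD+, baseline to Visit 16 | 15 | 53.7% | 38% | 54% to 15% |
| Both roles, baseline to Visit 16 | 31 | 79.6% | 63% | 79% to 28% |
| Omnibus ANOVAs, three samples | 46 | 90.6% | 74% | 91% to 37% |

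A rerun at correlation 0.5 agreed within about one percentage point.

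**The total-sample models.** With within-dyad correlation 0 the 46-ANOVA figure at correlation 0.5 is 70%, with about 46 × 0.05 = 2.3 false positives expected. At 0.3 it is 74%, with about 3.1. The difference arises because the total-sample model was simulated with dyad members treated as independent; the SAP does not say how it will handle the pairing.

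**Adding the rest.** Here the within-dyad correlation is 0, which is the proper null for section 4, and a five-visit ANOVA stands in for the follow-up ANCOVA. At between-measure correlations of 0, 0.5 and 0.9:

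- 92 models: 96%, 83%, 45%.
- 64 correlations alone: 96%, 87%, 50%, with 64 × 0.05 = 3.2 false positives expected.
- All 158: 99.9%, 98%, 72%.

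**The case against.** The best reply is that the exploratory status is already on the page. SAP 3.2 is headed as exploratory objectives and speaks of secondary and other exploratory ones, section 2 repeats that wording, and the correlations sit under an exploratory heading. Protocol 12.0 says that several domains are assessed for exploratory purposes. The study is a 10-dyad pilot not aimed at registration, and Protocol 12.1 concedes that even the primary may be underpowered. Formal correction is not essential in that setting.

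Much of this stands. There is a hierarchy of labels with one designated primary test; what is missing is a rule for reading the p-values below it. The labels do not supply one, because the 0.05 verdict covers all statistical tests.

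Four stronger readings that a reader might infer are not supported:

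- *That false positives among the section 2 contrasts are near certain.* Three visit pairs for each of the 46 models make 138 contrasts, and at correlation 0.5 about 95% to 97% of null trials would show at least one p ≤ 0.05. That assumes all pairs are tested, ungated and unadjusted, none of which the SAP specifies. If contrasts follow only a significant ANOVA, the figure is about 74%.
- *That the SAP will choose domains for the next trial by p-value.* SAP 2.0 speaks of the study's results in general.
- *That the percentages describe a treatment with no effect.* The simulated null is no change. In a single-arm study, scores can change without a treatment effect.
- *That a false positive is likely in any one family.* For the 15 PTSD+ tests alone the chance is below one half at correlation 0.5, and 15% at 0.9.

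**Conclusion.** The concern holds for the secondary and exploratory tests. Followed literally, the plan attaches an unqualified significance verdict to dozens of overlapping tests. If no measure changes, at least one false verdict has a chance of about 38% in the PTSD+ tests alone, 63% across both roles and 74% across the 46 ANOVAs, at an assumed between-measure correlation of 0.5 and within-dyad correlation of 0.3. Over between-measure correlations of 0 to 0.9 the ranges are 54% to 15%, 79% to 28% and 91% to 37%. The chance rises when the follow-up models and correlations are added, or if contrasts are not gated by the ANOVA.

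A reader might infer that the primary result is compromised as well. It is not: one contrast, one time point and one alpha are named, so multiplicity among the other tests leaves its 5% error untouched.

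**What to change.** 1. In SAP 6.0 and Protocol 12.0, limit the 0.05 significance rule to the primary CAPS-5 paired test.
2. State that p-values in SAP efficacy sections 2 to 4 are nominal, unadjusted and exploratory. Report each result as a mean change, or as r, with a 95% confidence interval.
3. In section 2, name baseline to Visit 16 within each role as the main reported contrast. Keep baseline to Visit 9 as a reported estimate with its interval, because change at the Midpoint is a stated objective (Protocol 3.2, SAP 3.2).
4. Reconcile the PCL-5 exemption. Once the rule covers only the primary test, the PCL-5 falls under item 2 with the other measures and both documents can say so.

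This does not make small p-values rarer under the null; it stops them from being reported as verdicts. It needs wording changes in two documents and no new data or tests. The cost is that the sponsor can no longer call an individual secondary result statistically significant.
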